
below for further explanation). Family members will also complete proxy-versions of the care satisfaction, quality of care, and therapeutic relationship measures identified above. At the symptom level, psychosis, negative symptoms, and general psychopathology will be assessed using the Brief Psychiatric Rating Scale (BPRS), and the Patient Health Questionnaire – 9 (PHQ-9). The Clinical Global Impression scale (CGI) will be administered to characterize overall illness severity. The Adolescent Alcohol and Drug Involvement Scale (AADIS)⁹⁵ will be administered to characterize current substance use.

Using videoconferencing software consistent with Project-ECHO infrastructure, all interviewer-rated assessments will be administered via live two-way video conferencing by trained interviewers, in a manner identical to the approach utilized in the original NAVIGATE trial²⁰. This method of remote assessment is comparable to in-person assessments for both patient acceptability and reliability⁵⁷.

As mentioned above, in order to capture caregiver perspective on the patient's functioning, we will have one of their caregivers/family members complete the proxy-administered version of the WHODAS and Life Skills Profile. Family members will also complete the OPOC, Youth Services Survey, and RSA. Family members will complete these at similar time points as patients complete their assessments (i.e. At baseline and after 6, 12, 18, and 24 months of the EPI program). They will complete these in self-report survey form.

Schedule of Assessments (Timeframe relates to the participants' 2 year timeframe in the clinic)					
Assessments	Admission to Clinic	Month 6	Month 12	Month 18	Month 24
Screening					
Informed Consent	•	**	**	**	**
Demographic form/SES	•	**	**	**	**
Eligibility/Termination Checklist	•	**	**	**	**
SCID 5 Baseline: Full SCID Month 12 and 24: Mood, Psychosis, Substance Use Disorders, Anxiety, and OCD Modules	•	**	•	**	•
Medical History	•	**	**	**	**
Clinical Assessments					
CGI	•	•	•	•	•
PHQ-9	•	•	•	•	•
BPRS	•	•	•	•	•
AADIS	•	•	•	•	•
Service Utilization					
SURF		•	•	•	•
Functional Assessments					
QLS	•	•	•	•	•
WHO DAS 2.0	•	•	•	•	•
WHO DAS 2.0 – proxy version, completed by family member/care giver	•	•	•	•	•
Life Skills Profile – proxy version, completed by family member/care giver	•	•	•	•	•
Satisfaction, Care Quality, and Therapeutic Relationship					
OPOC (participant and family member complete)	•	•	•	•	•

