Statistical Analysis: Our primary outcome is days in hospital in the year following NAVIGATE admission. We will compare the three groups (NAVIGATE, non-NAVIGATE EPI, and non-EPI FEP patients) across all covariates listed above. We will subsequently model total hospital days adjusting for covariates. The regression model will be determined by the distribution of the dependent variables. If normally distributed, linear regression; if the distribution assumes a Poisson distribution, we will use Poisson regression. Secondary outcomes will be modeled using logistic regression (for binary outcomes) or Cox Proportional Hazard modelling (for time-to-event outcomes).

Patient-Level Outcomes – Analytic/Statistical Plan (Objective 3):

Since this is an implementation study, based on the already established effectiveness of NAVIGATE, we do not have a comparator arm. We will compare patient level outcome data from our study with the aggregate data from the original NAVIGATE study to assess comparability of the intervention in different jurisdictions, using a matching-adjusted indirect comparison (MAIC) model. In this approach we adjust the population receiving the intervention to match the average baseline characteristics with a reference population. We then compare outcomes across balanced populations. This is facilitated by the use of identical patient-level outcome measures as in the RAISE study, and the collection of similar baseline characteristics that might influence outcome (e.g. age, education, sex, race, baseline illness severity). With a large number of patients, we will also explore sex-stratified analyses. Matching will be based on propensity score weighting. We will compare the primary patient-level outcome (total quality of life score) between our

NAVIGATE and the U.S. RAISE study NAVIGATE groups over two years (baseline, 6 months, 12 months, 18 and 24 months). At each time point, we will use percentage change in total QLS score, along with 95% confidence interval from the RAISE study and the present study. Using the MAIC approach, mean results with overlapping 95% confidence intervals are taken to indicate that the interventions produced equivalent results.

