With a sample size $n=400$ and repeated measures across five time-points (for QLS and BPRS), we will have the opportunity to identify subgroups of patients with different functional outcome and symptom trajectories using complex mixture modeling, namely latent class growth analysis (LCGA) and Latent Growth Mixture Modelling (LGMM). We can also model factors associated with outcomes in key subpopulations of interest. Given that 30% of individuals with first-episode psychosis disengage from services⁷⁴, measuring the effectiveness of implementation in specific at-risk subpopulations can help inform future adaptations of the intervention to better serve YEA with an FEP. These at-risk subpopulations include YEA without family involvement⁷⁴, those who use substances⁷⁴, homeless youth⁷⁵, youth from ethno-racial minority populations⁷⁶⁻⁷⁸, Indigenous youth^{79,80}, and sexual minority youth⁸¹. Service in more remote areas (especially at our north-eastern sites) may be an additional vulnerability factor. We have engaged the OSSU's Centre for Rural and Northern Health Research to incorporate some of these considerations. In addition, we have engaged OSSU Women's Xchange given sex-based differences in prevalence and illness severity.

Authentic Engagement of people with lived experience (Objective 4):

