activity inventory⁹⁴ as those that might most comprehensively evaluate engagement. In particular, the PPEET had the highest aggregate score on all categories, and includes a patient questionnaire (i.e. for service users, citizens, community representatives, and other stakeholders), a project questionnaire (i.e. for project lead, manager, or director), and an organization questionnaire (i.e. for senior leadership). We will administer a simplified PPEET and PCORI engagement activity inventory in addition to semi-structured interviews on a regular basis (e.g., monthly for PPEET and PCORI, less frequently for interviews)..

Building on Experiential Knowledge to Further Evaluate NAVIGATE from the Patient and Family Perspective: This particular approach will engage patients and family members to build on our qualitative work regarding acceptability, feasibility, and preference for NAVIGATE, i.e. coordinated, manualized EPI care, and will serve to engage those patients and family members who prefer more limited involvement (i.e. through interviews). Patients and family members participating in this process will be different than those participating on the advisory committee. Semi-structured interviews will be conducted 1-3 times during the NAVIGATE implementation process. By working alongside patients and families through engagement activities focused on the content and purpose of NAVIGATE, all stakeholders have the opportunity to contribute to the dialogue on its development. We will use a combination of purposive and convenience sampling strategies for the study⁹¹. Each site will help facilitate the recruitment of approximately three patient and two family member representatives, to ensure recruitment of approximately 20 male and female patients and family members in total. We will aim to include patients and families from diverse demographic, geographic, or socio-economic backgrounds: e.g. LGBTQ, rural, Indigenous, urban socio-economically disadvantaged and newly-immigrated populations.

5. Study Duration

The estimated length of time needed to complete the entire study (from enrolment of the first participant to completion of the last participant) is four years.

Termination of Participants from the Study:

Reasons for withdrawing individual participants from the study may include one or more of the following:

- a) Participant lost to follow-up.

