- b) Withdrawal of consent: **As this is a two part study, participants are free to withdraw consent in part or in entirety. Their participation in part or the entire study would be terminated accordingly.**
- c) inability to continue giving informed consent to participate in the research study

Any participant may be discontinued from the study at the discretion of the investigators if this is deemed to be in the best interest of the participant. The decision may be made either to protect the participant's health and safety, or because it is part of the research plan that people who develop certain conditions may not continue to participate.

Any research information recorded for, or resulting from, participation in this research study prior to the date that the participant formally withdrew their consent will be retained and may continue to be used and disclosed by the investigators for research purposes; however, no new data will be collected.

6. Risks/Benefits

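### The RAISE comparison balances patients at baseline but has no correction for selective loss afterwards, so QLS results at later visits need not compare balanced populations

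*Combined protocol and SAP*

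**What the plan says.** The analysis plan for Objective 3 (section 4, patient-level outcomes) compares the Ontario cohort with aggregate RAISE data "using a matching-adjusted indirect comparison (MAIC) model". The adjustment is described as follows: "In this approach we adjust the population receiving the intervention to match the average baseline characteristics with a reference population". The balancing variables are given as examples: "e.g. age, education, sex, race, baseline illness severity". The plan continues: "We then compare outcomes across balanced populations". The outcome is percentage change in total QLS at each visit up to 24 months, and overlap of the two studies' 95% confidence intervals is read as equivalence.

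The next paragraph turns to trajectory and subgroup modelling. It begins one sentence with "Given that 30% of individuals with first-episode psychosis disengage from services" and goes on to name at-risk groups, among them people who use substances and people without family involvement.

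Two collection rules bear on who has a QLS at a late visit. The schedule of assessments in section 3.3 is headed "Timeframe relates to the participants' 2 year timeframe in the clinic". Section 5 lists, among possible reasons for withdrawing a person, "Participant lost to follow-up" and "inability to continue giving informed consent to participate in the research study".

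**The concern.** Matching weights make the enrolled Ontario patients resemble RAISE on baseline averages. They do nothing about who is still assessed at month 12, 18 or 24. A percentage change at a visit needs a QLS at that visit, so without a further rule the comparison falls to whoever has one. If the people missing at late visits function differently from those seen, the balance achieved at baseline no longer holds.

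The plan itself gives reason to expect selective loss. Two of its named at-risk groups, substance users and people without family involvement, are not among the example balancing variables. Its only allowance for loss is about 25% before the first visit (section 3.3, recruitment). It makes none after enrolment and still counts 400 patients over five time points.

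At stake is the conclusion on the primary patient-level outcome. A real Ontario shortfall could be declared equivalent, and the people the plan most wants to learn about would be under-represented. The collection wording matters too, because a QLS that was never collected cannot be recovered by analysis.

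**Working it through.** **Inputs from the documents.** N = 400 recruited. The RAISE NAVIGATE arm is 223 (section 3.3). The RAISE total printed beside it is 423, but 223 + 181 = 404, which is the total in section 2.1; I use the arm size only. The equivalence rule is overlap of two 95% intervals.

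**Reproducing the plan's figure.** 100 + 400 × (1 − 0.25) = 400, which agrees with the target. The plan gives no margin, power or precision for the RAISE comparison, so there is nothing further to reproduce.

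**Assumptions (not in the documents).** A share p of patients has no QLS at month 24, and their mean change is D SD worse than that of those seen. SDs are equal in the two studies, matching costs no precision, and, for the table, RAISE is free of attrition bias. The last assumption is relaxed below.

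**Shift in the Ontario mean.** Full-cohort mean = (1 − p) × m + p × (m − D) = m − pD, where m is the mean of those seen. The observed mean is therefore too high by pD. At D = 0.5 this is 0.10 × 0.5 = 0.05, 0.20 × 0.5 = 0.10 and 0.30 × 0.5 = 0.15 SD. At p = 30% it is 0.075 SD for D = 0.25 and 0.225 SD for D = 0.75.

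**Effect on the overlap rule.** Let n = 400(1 − p). The intervals overlap when the observed difference is smaller in size than t = 1.96/√n + 1.96/√223. The standard error of the difference is s = √(1/n + 1/223). For a true full-cohort deficit of 0.3 SD, the expected observed difference is μ = −0.3 + pD, and P(overlap) = Φ((t − μ)/s) − Φ((−t − μ)/s).

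| p | n | t | s | P(overlap), D = 0 | P(overlap), D = 0.5 |
|---|---|---|---|---|---|
| 0 | 400 | 0.229 | 0.084 | 0.20 | 0.20 |
| 10% | 360 | 0.235 | 0.085 | 0.22 | 0.43 |
| 20% | 320 | 0.241 | 0.087 | 0.25 | 0.68 |
| 30% | 280 | 0.248 | 0.090 | 0.28 | 0.86 |

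The D = 0 column shows the effect of smaller numbers alone. The gap between the last two columns is due to selective loss.

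**Allowing for RAISE attrition.** If RAISE lost a share q with the same D, and its figures are observed-case, the net shift is (p − q) × D. With p = 30% and D = 0.5, q = 20%, 30% and 40% give +0.05, 0 and −0.05 SD. The documents do not give q, or say how RAISE handled missing data.

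**The case against.** The strongest reply is that several tempting readings go further than the text.

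- **That the plan expects 30% of QLS values to be missing.** It does not. The 30% is a cited rate of leaving services, used to motivate subgroup work. Leaving services is not a listed reason for withdrawal, interviewer ratings are done by video, and sections 2.1 and 6.2 report better retention under NAVIGATE than under usual care. A count of 280 at month 24 is therefore an illustration only.
- **That the plan prescribes an analysis of observed patients.** It is silent. Observed cases are the natural default, but this is an inference.
- **That Ontario will look too good against RAISE.** The direction is not established: equal loss with equal D cancels, and heavier loss in RAISE reverses the sign.
- **That one lapse in capacity ends participation.** Section 5 lists what reasons for withdrawal may include, and it ties the end of data collection to formal withdrawal of consent. Termination after a temporary lapse is permitted but not required. Likewise, the schedule heading sets the visit clock; it does not say that visits stop when someone leaves the clinic.

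The linked ICES data also still supply hospital and emergency outcomes for consenting patients who miss study visits.

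All of this stands, and it limits the size of the claim. It does not supply a method for missing QLS. The latent class and growth mixture models in section 4 serve a different aim, and nothing in the plan states or checks that loss in the two studies is alike.

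**Conclusion.** The concern holds in limited form. Following the plan as written gives a comparison that is balanced at baseline but made at each later visit among whoever has a QLS, with no correction for selective loss after enrolment. That does not support a claim of balanced populations, or of equivalence, at 24 months.

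The possible size matters well below 30% loss: at D = 0.5, losing 10% already raises the chance of calling a 0.3 SD deficit equivalent from 0.20 to 0.43. These figures rest on assumed p and D, equal SDs, no precision lost to weighting, and RAISE taken as free of attrition bias. The net bias against RAISE has unknown size and direction. The collection rules are ambiguous rather than wrong: they do not separate a temporary lapse from a permanent one, and nothing says that visits continue after a patient leaves the program. This should be changed, because it affects the primary patient-level outcome and the change is cheap.

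**What to change.** **Analysis plan, Objective 3.**
- At each visit, multiply the matching weight by an inverse-probability-of-being-observed weight, or use multiple imputation or a weighted mixed model.
- Build the observation model from baseline factors, including substance use (AADIS) and family involvement, and the latest earlier QLS and BPRS where one was due. It uses Ontario data only, so it does not need RAISE averages for these factors.
- Treat visits that late entrants were never due as not scheduled rather than missing. They have no earlier visits by design.
- Re-check balance against the RAISE baseline averages among those observed. Report retention and effective sample size at each visit.
- State whether the RAISE figures are observed-case or model-based, and show the Ontario result on the same basis. Correcting one side alone could create an imbalance.
- Add two sensitivity analyses: one without the observation weights, and a not-at-random analysis that shifts the missing outcomes by a range of deltas.

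**Schedule of assessments (section 3.3) and termination (section 5).**
- State that research visits remain due by time since EPI admission after a person leaves the program, offered by the existing video or remote route unless consent is withdrawn.
- State that a missed visit or a temporary inability to consent counts as a missed visit, with re-approach at the next one, subject to ethics board approval.

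**Cost.** One paragraph of analysis text and a sentence or two in each of the other sections. Intervals will widen from the extra weights, by an amount that cannot be stated before the effective sample size is known, and there will be some additional follow-up contacts.

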In 2004, the province of Ontario allocated funding for EPI programs based on early evidence of efficacy. Between 2005 and 2007, this new provincial funding led to a major EPI program expansion in Ontario²⁴, but the absence of provincial standards led to program development in an ad-hoc manner, drawing upon general service delivery experience and advice from established programmes²⁴. Concomitantly, the Early Psychosis Intervention Ontario Network (EPION) was established, which has now grown to 52 EPI sites. The establishment of EPI program standards²⁵ in Ontario in 2011, informed by existing international and national standards, but also by input from clinicians, patients, family-members, and policy makers was a crucial first step toward standardizing care. However, the release of standards alone is not sufficient to ensure effective implementation, practice change, and ongoing quality practice.

The Ontario Ministry of Health and Long Term Care established a Standards Implementation Steering Committee (SISC) within EPION that is supported by the Provincial System Support Program (PSSP), based at the Centre for Addiction and Mental Health (CAMH). The SISC was established due to increasing recognition that active support is required to implement and sustain evidence-based care in routine practice²⁶. Key findings from the first survey by the Ontario SISC of 52 EPI program sites in Ontario (92% participation) demonstrated important challenges in delivering evidence-based EPI care²⁷. A follow-up survey also identified opportunities for addressing these challenges²¹. Building on the two surveys, we conducted a study²⁸ to measure fidelity to current EPI standards using the First Episode Psychosis Service – Fidelity Scale (FEPS-FS)²⁹. This fidelity project trained EPI staff as peer assessors to document current service delivery approaches, challenges and support needs in self-selected EPION programs. Our most notable finding was lack of delivery of consistent recovery-oriented care, with no structured or manualized process for these elements of care. Through site visits, and in-person interviews with nine Ontario EPI programs, we obtained a richer and clearer picture of the current state, creating an opportunity to implement solutions that can address the major challenges identified in the fidelity study:

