In 2008, the National Institute of Mental Health (NIMH) issued a request for proposals entitled: Recovery After an Initial Schizophrenia Episode (RAISE), with a goal to change the trajectory and prognosis of FEP³⁰. NAVIGATE was developed in consultation with clinical and research experts, biostatisticians, health economists, consumers, family members, advocacy groups, and government officials. It is a form of coordinated specialty care for FEP consisting of 4 key intervention components: (i) individualized medication management using a decision support tool, (ii) a package of psychoeducation and a blend of evidence-based psychotherapies called “individual resiliency training” (IRT); (iii) supported employment and education (SEE); and (iv) a family education program. NAVIGATE was evaluated from 2009-2014 in a cluster randomized controlled trial involving 404 individuals with an FEP in 34 community mental health centers across the United States²⁰. Notably, it was delivered by re-allocating existing community mental health resources with no new funding for clinical care. Compared to usual care, NAVIGATE treatment provided greater improvement in symptoms, but more importantly, as prioritized by patients, significantly greater improvement in real-world functioning, including social functioning and engagement in educational and vocational training^{20,31}. NAVIGATE was also readily implementable across a broad range of community-based mental health settings, with enhanced engagement and delivery of multidisciplinary care to YEA presenting with psychosis and their families compared to standard care, and with longer and more consistent receipt of mental health services²⁰. A recent economic analysis revealed that NAVIGATE treatment was more cost-effective compared to standard community care, driven by the anticipated enhanced health benefits and improvements in quality of life³².

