Proctor's implementation outcomes⁶¹ will guide evaluation of implementation outcomes: three of the four CIHR implementation science metrics (adaptability, scalability, sustainability). Specifically we will assess i) fidelity (i.e. adaptability) to examine the extent to which programs operating in different contexts with different resources are able to implement NAVIGATE as intended. Second we will assess ii) penetration (i.e. scalability) the extent to which all eligible program patients receive NAVIGATE. Using the Consolidated Framework for Implementation Research (CFIR)⁶², we will assess contextual factors (stakeholder perceptions of acceptability, appropriateness, feasibility) that help or hinder use of NAVIGATE. Learning about these factors including how they relate to unique aspects across settings will inform wider efforts to adapt NAVIGATE and tailor implementation (adaptability and scalability). We will also assess iii) sustainability through uptake of the ECHO model. We address the fourth CIHR implementation science metric (affordability) in the System-Level outcome section further below.

i) Fidelity (ADAPTABILITY): We will use the First Episode Psychosis Service–Fidelity Scale (FEPS-FS)²⁹ to assess fidelity of service delivery to the current standard of EPI evidence-based practice in relation to 31 program-specific items (individual and team practices) on a 5-point scale from “not implemented” to “fully implemented”. Ratings for each site will be made by centrally located trained assessors through a remote assessment process that includes a review of site administrative data, data abstracted from client health records by trained abstractors, and phone interviews with site staff. The FEPS-FS was developed with a formal knowledge synthesis process rather than a single program model. It was used in the Ontario pilot and is relevant to the Ontario EPI standards. Reviews will be conducted at three points in time: during the exploration stage, after full implementation is reached and at the study end to assess sustainability. To examine fidelity results, site will be the unit of analysis. Descriptive statistics (percentages, means, medians, range) will be reported for the total scale score and for subscale scores that align with NAVIGATE

components. With a small number of sites, we cannot quantitatively test changes over time and across sites, but will describe and qualitatively compare findings.

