For additional validation of intervention delivery, fidelity scores will be calculated per site in relation to the four core NAVIGATE interventions (medication, IRT, SEE, family education) using the service utilization measure (see description in previous section). The Clinician Contact and Progress Note (a standard documentation template within NAVIGATE for IRT, SEE, and FEP components of treatment, captured in client health records, which captures information about which module was covered during each treatment session) will provide model adherence data for each patient across the core interventions. This will be augmented by the Service Use and Resource Form (SURF) that research staff will complete with each patient. We will mirror the original study, calculating the percentage of core modules completed per intervention per patient.

ii.a.) Penetration (SCALABILITY): Penetration assesses the extent to which eligible program patients receive the NAVIGATE treatments, and identifies any biases in delivery^{61,63}. This is important because a core aim of NAVIGATE is to increase consistency of model delivery across in patients across all programs. Fidelity to NAVIGATE will be calculated from the contact forms (clinician report) and the SURF (client report), and will be used to assess penetration and to identify variations in delivery across patients within sites and across sites. When assessing scalability, the unit of analysis will be the patient (n=400 patients). The outcome will be percentage of modules received for each of the four interventions and will be reported using percentages, means, medians, standard deviations, and interquartile ranges. A linear regression model will be used to identify predictors, with patient baseline characteristics such as sex, age, and illness complexity. The nesting of patients within each site will be accounted for in the analysis. All statistical tests will be two-tailed and statistical significance will be defined as p-values less than 0.05.

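### The plan specifies no allowance for clustering of patients within EPI programs in the Ontario 95% CI for QLS change, its primary patient-level outcome

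*Combined protocol and SAP*

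**What the plan says.** The subsection on patient-level outcomes (Objective 3) states: "We will compare the primary patient-level outcome (total quality of life score) between our" NAVIGATE patients and the NAVIGATE arm of RAISE, over two years. The method is a matching-adjusted indirect comparison (MAIC): "Matching will be based on propensity score weighting". The measure compared, visit by visit, is given as follows: "we will use percentage change in total QLS score, along with 95% confidence interval from the RAISE study and the present study". The decision rule is that "mean results with overlapping 95% confidence intervals are taken to indicate that the interventions produced equivalent results".

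No variance method is given for the Ontario interval. The subsection mentions no program effect, cluster-robust standard error or resampling of programs.

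Elsewhere the plan does recognise clustering:

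- Penetration (scalability), for the regression of percentage of modules received: "The nesting of patients within each site will be accounted for in the analysis".
- Fidelity (adaptability): "With a small number of sites, we cannot quantitatively test changes over time and across sites".
- Section 2.1 describes the reference study as a "cluster randomized controlled trial involving 404 individuals with an FEP in 34 community mental health centers".

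**The concern.** NAVIGATE is installed program by program and delivered by local teams, and section 3.3 stresses that sites differ. Patients in one program are therefore likely to have correlated QLS changes. Objective 3 asks whether the intervention performs comparably in another jurisdiction. On that reading, variation between programs is part of the sampling error of the Ontario mean. Weighting individuals to match baseline averages does not remove this correlation.

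The plan applies a nesting rule to a lesser analysis of the same patients and leaves it out here. That silence permits a default patient-level CI. If the ICC is not trivial, such an interval is too narrow. Variation between a few programs could then be read as a difference from RAISE.

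**Working it through.** The plan states no CI width, SD, ICC or precision target for QLS, so there is no figure to reproduce. The 400 is a recruitment sum (100 + 300), not a precision calculation.

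**Inputs**

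- Ontario n = 400 (section 3.3).
- RAISE NAVIGATE arm n = 223 (section 3.3).
- Number of programs K: not stated in the documents supplied. Upper value 9: participating programs all took part in the fidelity study, which involved "in-person interviews with nine Ontario EPI programs". Lower value 4: about 20 interviewees at about 5 per site (qualitative interviews, sections 4 and 12). Both are inferences.
- ICC: not stated. Assumed 0.01 to 0.05, with 0.001 as a near-zero case.
- Programs of equal size. Loss of precision from MAIC weighting is ignored; it would widen the interval further.

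**Formulas**

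- m = 400/K, which is 44.4 for nine programs and 100 for four.
- Design effect DE = 1 + (m − 1) × ICC.
- Ratio of correct to patient-level half-width = √DE.
- Coverage of the patient-level CI = 2Φ(1.96/√DE) − 1.
- Ratio with t-limits = √DE × t(0.975, K − 1)/1.96.

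**Results, n = 400**

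| K | ICC | DE | √DE | Coverage | Effective n | Ratio with t-limits |
|---|---|---|---|---|---|---|
| 9 | 0.001 | 1.04 | 1.02 | 94.5% | 383 | 1.20 |
| 9 | 0.01 | 1.43 | 1.20 | 89.8% | 279 | 1.41 |
| 9 | 0.05 | 3.17 | 1.78 | 72.9% | 126 | 2.10 |
| 4 | 0.001 | 1.10 | 1.05 | 93.8% | 364 | 1.70 |
| 4 | 0.01 | 1.99 | 1.41 | 83.5% | 201 | 2.29 |
| 4 | 0.05 | 5.95 | 2.44 | 57.8% | 67 | 3.96 |

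Example, K = 9 and ICC 0.05: DE = 1 + 43.4 × 0.05 = 3.17; √3.17 = 1.78; 2Φ(1.96/1.78) − 1 = 0.729.

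**Effect on the overlap rule at one visit, true means equal**

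Half-widths in SD units are 1.96/√400 = 0.098 for Ontario and 1.96/√223 = 0.131 for RAISE, so the intervals separate at a gap of 0.229 SD. With no clustering in either study, the chance of separation is 0.6%.

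Suppose both studies have ICC 0.05, the RAISE CI allows for it, and 17 of the 34 RAISE centres (an assumed half) delivered NAVIGATE. Then:

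- RAISE DE = 1 + (223/17 − 1) × 0.05 = 1.61, and its half-width is 1.96 × √(1.61/223) = 0.166.
- The gap needed with a patient-level Ontario CI is 0.098 + 0.166 = 0.264.
- Nine programs: true SE = √(3.17/400 + 1.61/223) = 0.123; 0.264/0.123 = 2.15; chance of false separation 3.2%.
- Four programs: true SE = √(5.95/400 + 1.61/223) = 0.149; 0.264/0.149 = 1.78; chance 7.5%.

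**Effect of widening the Ontario CI but keeping the overlap rule**

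At ICC 0.05 with t-limits the Ontario half-width is 0.205 (nine programs) or 0.388 (four). Adding 0.166 for RAISE, the gap needed for separation becomes 0.37 SD or 0.55 SD, against 0.229 SD when neither interval is adjusted.

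**The case against.** The strongest reply is that the plan is silent rather than wrong: it does not commit to a patient-level CI. That stands. The fault is an unspecified method where the plan specifies one elsewhere.

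Second, the size is not established. The manualised care is meant to reduce variation among sites, and remote rating by trained interviewers limits local rater effects. Both could keep the ICC low, and nothing in the documents supports 0.05 as a central value. This also stands. A reader might infer that the interval is certain to be far too narrow; the documents do not support that, because they give neither ICC nor program count.

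Third, fewer than 400 patients will contribute at some visits. Late entrants complete only some visits, and the plan cites 30% disengagement. With n = 280 (70% of 400) and ICC 0.05, coverage is 78% with nine programs and 65% with four. The problem is somewhat smaller but remains.

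Fourth, the programs were selected, not sampled, so an interval for patients of these programs alone could omit variation between programs. That is a legitimate estimand. It fits poorly with the stated purpose of comparing jurisdictions, and the plan does not declare it.

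Two further readings fail. A reader might infer that the RAISE interval is wrong too; the documents say only that RAISE was cluster randomised, not how its CI was computed. A reader might also infer that the omission leads to false claims of equivalence. Under the overlap rule a narrow CI pushes the other way, towards a false difference, and with nine programs that error is about 3% per visit in the case worked above.

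**Conclusion.** The omission is real: the CI for the primary patient-level outcome has no specified allowance for program clustering, although the same plan accounts for nesting in the penetration regression and says sites are few. If a patient-level CI is used, its half-width would be too small by a factor of 1.2 to 1.8 with nine programs and 1.4 to 2.4 with four. Coverage would run from about 90% down to 58%. These figures rest on n = 400, equal programs and an assumed ICC of 0.01 to 0.05. With an ICC near 0.001 the factor is 1.02 to 1.05 and the matter is negligible. The plan should settle the method in advance, because it cannot know which case applies.

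**What to change.** In the Objective 3 analytic plan:

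1. State that the MAIC-weighted Ontario QLS estimates will account for nesting of patients within programs. Use either a program random effect or a small-sample cluster-robust variance, with t-limits based on the number of programs.
2. State the number of programs, including how the north-east program with its sub-sites is counted. Report the ICC, noting that it will be imprecise with so few programs.
3. Use RAISE estimates whose standard errors allow for its site clustering, where available.
4. Replace the overlap rule with a CI for the Ontario-minus-RAISE difference that uses the clustering-adjusted standard error, judged against a prespecified margin. Items 1 to 3 adopted alone would make a conclusion of equivalence easier to reach.

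No new data are needed; the change is wording, a variance option and an agreed margin. The cost is precision. At ICC 0.05 with t-limits, the Ontario CI becomes about 2.1 times (nine programs) to 4.0 times (four programs) the patient-level width. For the difference, even normal limits give a half-width of 1.96 × 0.123 = 0.24 SD with nine programs or 1.96 × 0.149 = 0.29 SD with four, against 1.96 × √(1/400 + 1/223) = 0.16 SD if clustering is ignored in both studies. Equivalence may then not be demonstrable at a reasonable margin, and the plan should say so in advance.
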